5.5. Dose Justification

In Part A, a single dose of 120 mg will be used for the MR minitab formulations in a capsule and for the IR tablet. In Part B, it is planned to evaluate target daily doses of 30, 60 and 240 mg for 3 days. The selection of these dose levels are based on the doses being used in the ongoing Phase 2a studies (IR 60 mg BID) and the safety and PK data from the GSK2982772 FTIH study, where doses up to IR 120 mg BID for 14 days were administered.

In Part A, a single dose of 120 mg MR has been selected since this dose is anticipated to provide systemic exposure similar to the 60 mg BID regimen being used in the ongoing Phase 2a studies (assuming a relative bioavailability of 100%). In the GSK2982772 FTIH study, 120 mg of the IR formulation was well tolerated when administered as single and repeated doses (BID for 14 days). A single 120 mg dose of the MR formulation in a capsule is expected to result in lower C_{max} than for the 120 mg IR tablet, and overall systemic exposure (AUC) is expected to be similar or lower than a single 120 mg IR tablet dose.

The administration of 120 mg MR with food is expected to maintain AUC and C_{max} values within the range of values observed following 120 mg dose in the FTIH study. In the worst case scenario of dose dumping with food, 120 mg MR would have a PK profile similar to a single dose of 120 mg IR.

In Part B, the target daily MR doses of 30, 60, 240 mg reflect the approximate dose range that is planned to be taken forward into the Phase 2b DR studies. The actual dose level may be increased (by adding additional minitabs to the capsule or by giving multiple capsules) if the relative bioavailability of the selected MR at 120 mg is less than 100% compared to a 120 mg dose of the IR tablet. Taking into account the bioavailability of MR relative to IR, it is planned that the highest dose of MR to be administered will be not exceed a total daily dose equivalent to 240 mg IR (e.g. if the bioavailability of MR is 50% that of IR, the maximum daily dose of MR to be administered would be 480 mg).

In Part C, the target doses are higher than previously evaluated in Parts A and B to reflect a revised estimate of the upper limit of the dose range to be taken forward in the Phase 2b DR studies which for the IR formulation equates to 240 mg TID (720 mg/day). This IR dose regimen has been evaluated following 1 day of dosing in healthy participants in Study 205184 and was shown to be well tolerated. The highest target dose is currently 960 mg which was predicted assuming the bioavailability of MR tablet relative to IR is the same as observed for the slowest minitab formulation in the fasted state ($F_{rel} = 74\%$). The highest dose level may be adjusted based on observed relative bioavailability of the MR tablet but will not exceed the GSK2982772 systemic exposure associated with the

single day administration of 240 mg IR TID (i.e. mean AUC of 45.0 µg.h/mL and mean C_{max} of 4.3 µg/mL).

6. STUDY POPULATION

Prospective approval of protocol deviations to recruitment and enrolment criteria, also known as protocol waivers or exemptions, is not permitted.

Quotient Sciences must have a full medical history from each participant's general practitioner within the last 12 months, prior to enrolment in the study. Participants will be recruited from the Quotient Sciences panel or by direct advertising to the public.

Before participants are admitted to the clinic, The Over Volunteering Prevention System will be checked to ensure that each participant has not participated in a study at another site within at least 3 months of the dosing date.

6.1. Inclusion Criteria

Participants are eligible to be included in the study only if all of the following criteria apply:

Age

1. Participant must be 18 to 65 years of age inclusive, at the time of signing the informed consent.

Type of Participant and Disease Characteristics

2. Participants who are overtly healthy as determined by medical evaluation including medical history, physical examination, laboratory tests, and cardiac monitoring.

Weight

3. Body weight ≥ 50 kg and body mass index within the range 19.0 to 32.0 kg/m² (inclusive).

Sex

4. Male or female

a. Male participants:

A male participant must agree to use a highly effective contraception as detailed in [Appendix 5](#) of this protocol during the treatment period and for at least 90 days after the last dose of study treatment and refrain from donating sperm during this period.

b. Female participants:

A female participant is eligible to participate if she is not pregnant (see [Appendix 5](#)), not breastfeeding, and at least one of the following conditions applies:

- (i) Not a woman of childbearing potential (WOCBP) as defined in [Appendix 5](#)

OR

- (ii) A WOCBP who agrees to follow the contraceptive guidance in [Appendix 5](#) during the treatment period and for at least 30 days before and 30 days after the last dose of study treatment.

Informed Consent

5. Capable of giving signed informed consent as described in [Appendix 3](#) which includes compliance with the requirements and restrictions listed in the ICF and in this protocol.

6.2. Exclusion Criteria

Participants are excluded from the study if any of the following criteria apply:

Medical Conditions

1. History of or current cardiovascular, respiratory, hepatic, renal, gastrointestinal (GI), endocrine, haematological, or neurological disorders capable of significantly altering the absorption, metabolism, or elimination of drugs; constituting a risk when taking the study treatment; or interfering with the interpretation of data.
2. Parts A and C only: Any history of suicidal behaviour within the past 6 months or any history of attempted suicide in a participant's lifetime.
3. Part B only: Participants with current history of Suicidal Ideation Behaviour as measured using the C-SSRS or a history of attempted suicide.
4. History of clinically significant psychiatric disorders as judged by the investigator. Depression requiring treatment in the last 2 years.
5. History of herpes zoster (shingles) reactivation.
6. History or diagnosis of obstructive sleep apnoea.
7. History of a significant respiratory disorder. Childhood asthma that has fully resolved is permitted.
8. History or current evidence of febrile seizures, epilepsy, convulsions, significant head injury, or other significant neurologic conditions.
9. A positive diagnostic tuberculosis (TB) test at screening defined as a positive QuantiFERON-TB Gold test or T-spot test. In cases where the QuantiFERON or T-spot test is indeterminate, the participant may have the test repeated once, but they will not be eligible for the study unless the second test is negative.
10. History of GI surgery (with exception of appendectomy).
11. History of cholecystectomy or gall stones.
12. Presence or history of clinically significant allergy requiring treatment, as judged by the investigator. Hayfever is allowed unless it is active.
13. Alanine transaminase (ALT) >1.5x upper limit of normal (ULN).
14. Bilirubin >1.5xULN (isolated bilirubin >1.5xULN is acceptable if bilirubin is fractionated and direct bilirubin <35% of total).

15. Current or chronic history of liver disease, or known hepatic or biliary abnormalities (with the exception of Gilbert's syndrome).
16. Corrected QT interval (QTc) >450 milliseconds (msec).

Notes:

- The QTc is the QT interval corrected for heart rate according to either Bazett's formula (QTcB), QT interval corrected for heart rate according to Fridericia's formula (QTcF), or another method, machine or manual over read.
- The specific formula that will be used to determine eligibility and discontinuation for an individual participant should be determined prior to initiation of the study. In other words, several different formulae cannot be used to calculate the QTc for an individual participant and the lowest QTc value used to include or discontinue the participant from the trial.
- For purposes of data analysis, QTcB, QTcF, another QTc correction formula or a composite of available values of QTc will be used as specified in the Reporting and Analysis Plan.

Prior/Concomitant Therapy

17. Past or intended use of over-the-counter or prescription medication including herbal medications within 7 days prior to dosing (paracetamol/acetaminophen [up to 2 g per day], hormone replacement therapy and hormonal contraception are permitted).
18. Live or attenuated vaccine(s) within 30 days of enrolment, or plans to receive such vaccines during the study or plans to receive a vaccine within 30 days + 5 half-lives of the last dose of study medication.

Prior/Concurrent Clinical Study Experience

19. Participation in the study would result in loss of blood or blood products in excess of 500 mL within a 56 day period; therefore donation or loss of greater than 400 mL of blood within the previous 3 months.
20. Exposure to more than 4 new chemical entities within 12 months prior to the first dosing day.
21. Current enrolment or past participation within the last 3 months before signing of consent in this or any other clinical study involving an investigational study treatment or any other type of medical research.
22. Participants who have previously been enrolled in this study. Participants in Part A of this study are not permitted to participate in Part B. Participants in Parts A or B of this study are not permitted to participate in Part C.

Diagnostic assessments

23. Current or history of renal disease or estimated glomerular filtration rate (GFR) by Chronic Kidney Disease Epidemiology Collaboration (CKD-EPI) equation calculation <60 mL/min/1.73m² at screening.
24. Presence of Hepatitis B surface antigen (HBsAg) at screening Positive Hepatitis C antibody test result at screening or within 3 months prior to first dose. As potential

for and magnitude of immunosuppression with this compound is unknown, participants with presence of hepatitis B core antibody (HBcAb) should be excluded. Participants positive for HBsAg and/or positive for anti-HBc antibody (regardless of anti-HBs antibody status) are excluded.

25. An elevated C-reactive protein (CRP) outside the normal reference range.
26. Part B only: A positive anti-nuclear antibody (ANA) outside the normal reference range.
27. Confirmed positive pre-study drug/alcohol screen.
28. Positive human immunodeficiency virus (HIV) antibody test.
29. Regular use of known drugs of abuse, or history of drug or alcohol abuse in the past 5 years.

Other Exclusions

30. Regular alcohol consumption within 6 months prior to the study defined as an average weekly intake of >21 units for males or >14 units for females. One unit is equivalent to 8 g of alcohol: a half-pint (~240 mL) of beer, 1 glass (125 mL) of wine or 1 (25 mL) measure of spirits.
31. Current use or history of regular use of tobacco- or nicotine-containing products within 6 months prior to screening. A carbon monoxide breath test reading of greater than 10 parts per million (ppm).
32. Sensitivity to any of the study treatments, or components thereof, or drug or other allergy that, in the opinion of the investigator or medical monitor, contraindicates participation in the study.
33. Unwilling or unable to swallow multiple size 0-00 capsules as part of study participation.
34. Participants who do not have suitable veins for multiple venepunctures/cannulation as assessed by the investigator at screening.
35. Total cholesterol ≥ 300 mg/dL (≥ 7.77 millimole [mmol]/Liter [L]) or triglycerides ≥ 250 mg/dL (≥ 2.82 mmol/L).
36. Participants who are study site employees, or immediate family members of a study site or sponsor employee.

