Brief physical examination		X		X ²	X	2. Discharge (32 h post-dose for Treatment Period 1, 2, 4, 5 and 6 in Part A and Treatment Period 1, 3, 4, 5 and 6 in Part C 24 h post-dose for Treatment Period 3 in Part A and Treatment Period 2 Part C)
Medical history (includes substance usage) ³	X					3. Substances: Drugs, Alcohol, tobacco and caffeine
Past and current medical conditions	X					

Procedure	Screening (up to 28 days before Day 1)	Treatment Period 1, 2, 3, 4, 5, 6 Day			Follow-up/Study Discontinuation (7 days post last dose)	Notes ^a
		-1	1	2		
Follicle Stimulating Hormone (FSH) (as needed in women of non-childbearing potential only)	X					
Serum pregnancy test (WOCBP only)	X			X	X	
Urine pregnancy test (WOCBP only)		X				
Human Immunodeficiency Virus (HIV), Hepatitis B and C screening ⁴	X					4. If test otherwise performed within 3 months prior to first dose of study treatment, testing at screening is not required
Tuberculosis (TB) Test	X					
Urine drug screen	X	X				
Alcohol breath test	X	X				
Carbon monoxide breath test	X	X				
Laboratory assessments (haematology, clinical chemistry and urinalysis)	X	X	X ⁵	X ⁵	X	5. Pre-dose (Treatment Period 1 only) and 24 h post-dose Allowable windows in Section 9.4.4
Glomerular filtration rate	X					
C-reactive protein (CRP)	X					

Procedure	Screening (up to 28 days before Day 1)	Treatment Period 1, 2, 3, 4, 5, 6 Day			Follow-up/Study Discontinuation (7 days post last dose)	Notes ^a
		-1	1	2		
12-lead ECG	X ⁶	X	X ⁷	X ⁸	X	6. In triplicate 7. Pre-dose and 2 and 12 h post-dose 8. 24 h post-dose Allowable windows in Section 9.4.3
Vital signs	X	X	X ⁹	X ¹⁰	X	9. Pre-dose and 2 and 12 h post-dose 10. 24 h post-dose Allowable windows in Section 9.4.2
Study treatment			X			
AE review		←=====→			X	
Serious AE (SAE) review	X	←=====→			X	
Concomitant medication review		←=====→			X	
PK blood sample collection			X ¹¹	X ¹¹		11. Time points in Table 2

^a The timing of assessments may be amended in Part C if BID dosing is selected for any of the regimens.

Table 2 Pharmacokinetic Blood Sample Collection Times – Parts A and C

		Part A Treatment Periods 1, 2, 4, 5 and 6 (MR Formulations) Part C Treatment Periods 1, 3, 4, 5 and 6 (MR Formulations)																
Time (h)	Pre-dose	0	2	4	6	8	10	12	14	16	18	20	22	24	26	28	30	32
Dosing		X																
PK sampling	X		X	X	X	X	X	X	X	X	X	X	X	X	X	X	X	X
		Part A: Treatment Period 3 (IR Formulation) Part C: Treatment Period 2 (IR Formulation)																

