9. STUDY ASSESSMENTS AND PROCEDURES

- Study procedures and their timing are summarized in the SoA.
- Protocol waivers or exemptions are not allowed.
- Immediate safety concerns should be discussed with the sponsor immediately upon occurrence or awareness to determine if the participant should continue or discontinue study treatment.
- Adherence to the study design requirements, including those specified in the SoA, is essential and required for study conduct.
- All screening evaluations must be completed and reviewed to confirm that potential participants meet all eligibility criteria. The investigator will maintain a screening log to record details of all participants screened and to confirm eligibility or record reasons for screening failure, as applicable.
- Procedures conducted as part of the participant's routine clinical management or by generic screening (e.g., blood count) and obtained before signing of ICF may be utilized for screening or baseline purposes provided the procedure met the protocol-specified criteria and was performed within the time frame defined in the SoA.
- The maximum amount of blood collected from each participant over the duration of the study, including any extra assessments that may be required, will not exceed 550 mL in a 56-day period.
- Repeat or unscheduled samples may be taken for safety reasons or for technical issues with the samples.
- A participant will be allowed to leave the premises following completion of study-specific procedures at 32 hours post-dose (Part A, Treatment Periods 1, 2, 4, 5, 6 and Part C, Treatment Periods 1, 3, 4, 5, 6) or 24 hours post-dose (Part A, Treatment Period 3 and Part C, Treatment Period 2) or 24 hours after the last dose (Part B Treatment Periods 1, 2 and 3; if BID dosing selected this will be after the last evening dose) providing that:
 - No AEs have been reported during the study visit
 - The participant responds positively when asked “How are you feeling?”

If any of these conditions are not met, then the participant may only be allowed to leave the clinical unit with the authorisation of the investigator or appropriately qualified delegate.

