9.5. Pharmacokinetics

- Blood samples of approximately 2 mL will be collected for measurement of plasma concentrations of GSK2982772 as specified in the SoA (see Section 2). Instructions for the collection and handling of biological samples will be provided by the sponsor. The actual date and time (24-hour clock time) of each sample will be recorded.
- Processing, storage and shipping procedures are provided in the Study Reference Manual (SRM) or equivalent.
- The acceptable deviations from the nominal post-dose blood sampling times are as follows:
 - The pre-dose blood sample will be taken ≤ 1 hour before dosing.
 - Post-dose samples will be taken within ± 10 minutes of the nominal post-dose sampling time
- Samples will be used to evaluate the PK of GSK2982772. Samples collected for analyses of GSK2982772 plasma concentration may also be used to evaluate safety aspects related to concerns arising during or after the study.
- Genetic analyses will not be performed on these plasma samples. Participant confidentiality will be maintained.

Plasma analysis will be performed under the control of Platform Technology & Science (PTS), In Vitro/In Vivo Translation (IVIVT) and Third Party Resourcing (TPR), GSK. Concentrations of GSK2982772 will be determined in plasma using the current approved bioanalytical methodology. Raw data will be archived at the Bioanalytical site as detailed in the SRM or equivalent.

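### The 500 mL and 550 mL blood limits disagree, and criterion 19's 400 mL prior-loss cut-off does not guarantee the 500 mL limit it is derived from

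*Protocol*

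**What the plan says.** Criterion 19 in Protocol Section 6.2 has two clauses. The first sets the limit: "Participation in the study would result in loss of blood or blood products in excess of 500 mL within a 56 day period". The second presents a working rule as its consequence: "therefore donation or loss of greater than 400 mL of blood within the previous 3 months". A prior loss of exactly 400 mL is therefore allowed.

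Section 9 sets a different ceiling. Its subject is "The maximum amount of blood collected from each participant over the duration of the study, including any extra assessments that may be required", and the amount "will not exceed 550 mL in a 56-day period".

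Section 9.5 gives the sample size: "Blood samples of approximately 2 mL will be collected for measurement of plasma concentrations of GSK2982772". Table 2 gives the sampling times for Parts A and C, and Table 4 those for Part B. The protocol gives no volume for a safety-laboratory draw and no planned total for any part. It does not show how 400 mL follows from 500 mL. Sections 6 and 9 both rule out waivers.

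**The concern.** There are two separate problems.

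- **The limits differ over the same window.** A participant from whom the study collects between 501 and 550 mL in 56 days complies with Section 9, yet has lost more through participation than criterion 19 accepts.
- **The cut-off is presented as following from the 500 mL limit, but does not protect it.** It leaves the study 100 mL, and the sampling tables schedule more than that in PK blood alone.

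At stake is a protection for healthy volunteers who, by Section 3.3.2, have no intended direct health benefit. A recent donor can pass the explicit cut-off and then exceed 500 mL in 56 days simply by following the schedule. The site has no stated blood volume with which to notice this at screening.

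**Working it through.** The plan gives no total to reproduce, so this is a direct count.

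**Inputs.** About 2 mL per PK sample (Section 9.5); sampling times from Tables 2 and 4; minimum of 7 days between doses in Parts A and C, and of 7 days from the last morning dose to the next period's first dose in Part B (Section 5.1).

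**PK volume per period**
- MR period, Parts A and C: pre-dose + 16 times (2 to 32 h, every 2 h) = 17 samples; 17 × 2 = 34 mL.
- IR period, Parts A and C: pre-dose + 12 times = 13 samples; 13 × 2 = 26 mL.
- Part B period: pre-dose + 12 times = 13 samples on each of Days 1 and 3; 2 × 13 × 2 = 52 mL.

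**Totals with a permitted 400 mL prior loss**

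| Schedule | PK blood | Plus 400 mL | Over 500 mL by |
|---|---|---|---|
| Part A or C, six periods | 5 × 34 + 26 = 196 mL | 596 mL | 96 mL |
| Part A, Periods 5 and 6 cancelled | 3 × 34 + 26 = 128 mL | 528 mL | 28 mL |
| Part B, three periods | 3 × 52 = 156 mL | 556 mL | 56 mL |

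**When the 56-day window is shared.** Let Day 1 be first dosing and L the day of the last draw counted. A loss d days before Day 1 falls in the same 56 days if d + L ≤ 56.
- Parts A and C, first excess on PK blood alone: three periods give 34 + 34 + 26 = 94 mL (494 mL with the prior loss); the fourth brings 128 mL (528 mL). At 7-day spacing Period 4 is dosed on Day 22 and its last draw is on Day 23, so d ≤ 33. At 11-day spacing the last draw is on Day 35, so d ≤ 21.
- Parts A and C, full 596 mL: at 7-day spacing Period 6 is dosed on Day 36 and ends on Day 37, so d ≤ 19.
- Part B: Period 2 starts on Day 3 + 7 = 10 and its last draw is on Day 13, with 2 × 52 = 104 mL taken (504 mL with the prior loss), so d ≤ 43. Period 3 starts on Day 19 and ends on Day 22, so the full 556 mL needs d ≤ 34.

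**Safety blood.** Table 1 schedules 15 laboratory sessions in Parts A and C: screening 1, Day -1 × 6, Period 1 pre-dose 1, 24 h × 6, follow-up 1. The exact volumes do not matter to the finding. By the end of Period 3, seven of these have occurred after screening (Day -1 × 3, one pre-dose, 24 h × 3). At only 1 mL each, 400 + 94 + 7 = 501 mL.

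**In-study blood alone**, which is what Section 9 counts. Assuming 5 to 15 mL per session, 15 sessions take 75 to 225 mL. Then 196 + 75 = 271 mL and 196 + 225 = 421 mL. At an assumed 20 mL, 196 + 300 = 496 mL. All are below both 500 and 550 mL.

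**The case against.** The case on the other side has five parts.

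- **The limits have different roles.** Criterion 19 is an entry test and Section 9 a ceiling on conduct with room for repeats. On the assumed laboratory volumes, scheduled in-study blood reaches neither. This stands as a limit on the practical effect, but it does not make the two figures agree.
- **Criterion 19's first clause might catch the recent donor by itself.** It might, if a site reads it as a separate test that includes prior loss. To apply it the site would need the planned volume, which is not stated, while the explicit cut-off admits the person.
- **The scenario is narrow.** The look-back is 3 months and the limit covers 56 days, so a loss early in the look-back causes no excess. Seven days is a minimum, and the interim reviews may lengthen the gaps. This stands, and is why the windows are given above.
- **Parts A and B are complete** (Section 3.1). Their totals show the same defect, but a change would now act only on Part C.
- **Part C or Part B sampling may be reduced under BID dosing** (footnotes to Tables 2 and 4). This could lower the affected totals somewhat.

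A reader might go further and infer that 596 mL also breaches the 550 mL limit, by 46 mL. The text does not support that: the Section 9 limit covers blood collected in the study and does not mention earlier donation. A reader might also infer that sites would drop late PK samples because they face two ceilings. Nothing supports that either, since planned in-study volumes stay below both. Finally, adding all 15 safety draws to 596 mL would overstate a 56-day total. Screening up to 28 days before Day 1, 35 days from first to sixth dose and a follow-up 7 days later can span 28 + 35 + 7 = 70 days.

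**Conclusion.** The point holds in two parts. First, the 500 mL and 550 mL limits conflict as written. Second, the 400 mL cut-off does not guarantee the 500 mL limit: every schedule considered exceeds it on PK blood alone, by 28 to 96 mL, for someone at the cut-off whose loss shares the 56-day window with the draws.

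This rests on 2 mL per sample, completion of the scheduled samples, and counting prior loss towards the 500 mL limit, which the second clause of criterion 19 implies. In Parts A and C at the shortest spacing, an excess on PK blood alone needs a loss within about 33 days before first dosing, and the full 596 mL needs one within about 19 days. A breach of the 550 mL limit is not shown. The matter is an inconsistent eligibility threshold. It has no demonstrated effect on the PK data or the analysis.

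**What to change.** Reconcile criterion 19 with Section 9, and state for each limit whether blood lost before the study counts. State the planned total blood volume per part, PK plus safety laboratory, ideally beside Tables 2 and 4. Then make the prior-loss cut-off and its look-back consistent with the limit and the planned draw. The limit, the cut-off and the look-back are for the sponsor and ethics committee to set; no values are proposed here.

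The cost is protocol wording and one volume calculation per part, through whatever amendment route applies. Depending on the values chosen, a few recent donors may be deferred at screening. Sampling times and analyses need not change.
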